## 9. ADVERSE EVENTS AND UNANTICIPATED EVENTS

### 9.1 Adverse Event Definition

An adverse event is any untoward or unfavorable physical or psychological occurrence in a human subject, including any abnormal sign (for example, abnormal physical exam or laboratory finding), symptom, or disease temporally associated with the subject's participation in the research, whether or not considered related to the subject's participation in the research.

Toxicity will be scored using CTCAE Version 5.0 for toxicity and adverse event reporting. A copy of the CTCAE Version 5.0 can be downloaded from the CTEP homepage ([HTTP://CTEP.INFO.NIH.GOV](http://CTEP.INFO.NIH.GOV)). All appropriate treatment areas will have access to a copy of the CTCAE Version 5.0. All adverse clinical experiences, whether observed by the investigator

or reported by the subject, must be recorded, with details about the duration and intensity of each episode, the action taken with respect to the test drug, and the subject's outcome. The investigator must evaluate each adverse experience for its relationship to the test drug, its expectedness, and for its seriousness.

The investigator must appraise all abnormal laboratory results for their clinical significance. If any abnormal laboratory result is considered clinically significant, the investigator must provide details about the action taken with respect to the test drug and about the subject's outcome.

## **9.2 Serious Adverse Event (SAE) Definition**

**Serious Adverse Event:** According to the FDA's Code of Federal Regulations Title 21 Part 314.80, a SAE is any untoward medical occurrence that results in any of the following outcomes:

- Death
- A life-threatening event (an event that places the subject at immediate risk of death from the event as it occurred)
- Inpatient hospitalization or prolongation of an existing hospitalization
- A persistent or significant disability / incapacity
- A congenital anomaly / birth defect
- Important medical events based upon appropriate medical judgment that may jeopardize the patient or subject and may require medical or surgical intervention to prevent one of the outcomes listed in this definition of serious.

**Expectedness:** Unexpected events include any adverse drug experience that is not listed in the current package insert for the drug product (e.g., all previously unobserved or undocumented events).

**Relatedness:** Indicates that a determination has been made that an event had a reasonable possibility of being related to exposure to the product. Examples of causality include not related, unlikely, possibly, probable, definitely related and unable to be determined.

## **9.3 Unanticipated Problem (UP) Definition**

Unanticipated Problem is defined as an event, experience or outcome that meets **all three** of the following criteria:

- is unexpected; AND
- is related or possibly related to participation in the research; AND
- suggests that the research places subjects or others at a greater risk of harm (including physical, psychological, economic, or social harm) than was previously known or recognized.

Death due to progressive COVID infection will not be considered an unexpected event.

Reporting of AEs, SAEs, and UPs to the IRB and FDA will take place according to institutional IRB and FDA policy (see Section 10). AEs and SAEs will be reported from the first dose of study drug through hospital discharge. All SAEs should continue to be monitored until they are

resolved or are clearly determined to be due to a patient's stable or chronic condition or intercurrent illness(es).

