## **2.5 Secondary Objectives**

- Overall Survival at 30 days is a key secondary endpoint.
- Improvement in inflammatory markers associated with cytokine storm (Ferritin, C-Reactive Protein (CRP), d-dimer, white blood cell count)
- Cumulative incidence of grade 3 and 4 adverse events during hospitalization
- Cumulative incidence of serious adverse events during hospitalization
- Duration of hospitalization
- Duration of ventilation
- Ventilator free days (reintubations or death within 28 days will result in zero ascribed time off ventilator prior to reintubation)
- Improvement in oxygenation or paO2/FIO2 ratio

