## **4. INVESTIGATIONAL PLAN**

### **4.1 Overall Design**

Open-label, randomized Phase II study of etoposide administered intravenously at a dose of 150 mg/m^2 once daily on Days 1 and 4 for a total of two doses to inpatient patients with moderate and severe COVID-19 who have consented to treatment on this clinical trial. Dose reductions will be performed as outlined in Section 5.

This study includes a screening period, a treatment period, and a follow-up period for adverse events that will include the remainder of hospitalization, with additional assessments at days 30 and 60 as outlined in the study calendar (Section 6). After obtaining informed consent, the patients randomized to etoposide will begin treatment with the study drug. Subjects randomized to control will receive standard of care treatment. No placebo will be used. Subjects will be monitored for adverse events and to evaluate study outcomes. Patients removed from the study due to any unacceptable adverse events will also be followed until time of death or hospital discharge.

For patients randomized to standard of care, day 1 will be considered day of randomization. These patients will be followed to record the outcome of all primary and secondary objectives until time of death or hospital discharge, whichever occurs earlier.

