## **5.4 Etoposide Expected Toxicities and Management**

Reversible myelotoxicity has been uniformly observed to be the major toxicity for VP-16 and to represent the only clinically significant side effect. Following a single IV injection, peak myelotoxicity occurs at seven to nine days. Following daily injections for five to seven days, myelotoxicity is maximal between 12-16 days from the initiation of therapy. Bone marrow suppression is mainly manifested as granulocytopenia, with thrombocytopenia and anemia occurring to a lesser extent. Gastrointestinal toxicities including transient modest nausea, vomiting, and diarrhea, are common. Other reactions could include aftertaste, rash, pigmentation, pruritis, abdominal pain, constipation, and dysphagia. Occasional alopecia is reported. VP-16 does not produce phlebitis or nephrotoxicity. Rarely anaphylactic-like reactions have been reported, as well as, hypotension. The drug is to be infused over 60 minutes in this study to decrease the potential for hypotension, and the blood pressure and pulse will be monitored during the infusion. Occasionally, chills, fever, peripheral neurotoxicity, stomatitis, hepatotoxicity, transient cortical blindness and radiation recall dermatitis may be a result of VP-16 administration. Stomatitis is usually associated with high dose regimens containing etoposide. The occurrence of acute leukemia has been reported rarely in patients treated with VP-16 in association with other antineoplastic agents. Etoposide can cause fetal harm when administered to a pregnant women. It has been shown to be teratogenic in mice and rats. In females of reproductive potential, etoposide may cause infertility and result in amenorrhea. Premature menopause can occur with etoposide. Recovery of menses and ovulation is related to

age at treatment. Males In male patients, etoposide may result in oligospermia, azoospermia, and permanent loss of fertility. Sperm counts have been reported to return to normal levels in some men, and in some cases, have occurred several years after the end of therapy Secondary leukemias associated with etoposide have been reported. Women of childbearing potential will be advised to avoid becoming pregnant for at least 6 months after the final dose of etoposide. Males with female partners of reproductive potential will be advised to use effective contraception for 4 months after the final etoposide dose.

Safety of etoposide for use by nursing women has not been established.

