## 6. STUDY PROCEDURES & CALENDAR

REQUIRED STUDIES	Screening	Day 1, Day 4 and Day 7 Σ#	Prior to discharge	Day 30*
PHYSICAL				
History & Physical Exam	X	X	X	X
Height, Weight, Body Mass Index, and Body Surface Area	X			
Vital Signs	X	X	X	X
Toxicity Notation	X	X	X	X
Respiratory Status on 8 point scale ^	X	X	X	X
HISTORY				
Concomitant medicines (including COVID therapies, ie hydroxychloroquine, tocilizumab, anakinra) with date of initiation	X			
Smoking status	X			
Comorbidities	X			
Symptoms, including date of symptom onset	X			
LABORATORY				
Beta HCG (for women of childbearing potential)	X			
CBC with Differential +	X	X	X	X
Comprehensive metabolic panel +	X	X	X	X
Lactate Dehydrogenase	X	X	X	X
D-dimer	X	X	X	X
Ferritin	X	X	X	X
C-reactive protein	X	X	X	X
PaO 2 /FIO 2 (P/F) ratio (cohort 2 only)	X	X	X	X
INR (if on warfarin) Ω	X			
ADDITIONAL TESTING				
Electrocardiogram (ECG)	X			

# For subjects randomized to treatment, the data for Day 1 and Day 4 will be collected prior to the etoposide dose (within 24 hours).

\*Information to be obtained as feasible, if patient has been discharged attempts will be made to obtain the information from the patient's primary care provider. If such results are not available, participant will be contacted by the research nurse to assess toxicities.

^ Mortality assessment (included on the 8 point scale) will also be recorded at Day 14 and 60, in addition to Day 30 mentioned above

+ CBC and comprehensive metabolic panel will be measured at least twice weekly during hospitalization. These tests will also be obtained pre-dose 8, 11, 18, and 25 for those patients who require additional etoposide dosing as described above (Section 4.3 and 5.3)

Ω INR to be repeated at least twice weekly for patients on warfarin

Σ Day 1 of treatment for patients randomized to standard of care (SOC) will be considered the day of randomization

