## 7.2 Statistical Analysis

Tabulations overall, and by treatment group, will be produced for appropriate demographic, baseline, efficacy, and safety parameters, with number and percentages reported for categorical variables and the mean, median, standard deviation, and range for continuous variables. All analyses will be performed at an  $\alpha=0.05$  level using SAS v.4.

Efficacy analyses will be performed in an intention-to-treat (ITT) population consisting of all patients randomized. The difference in ordinal scale improvement rates between treatment arms will be calculated with a 95% confidence interval and formally compared using Fisher's Exact Test. For secondary analysis of the primary endpoint, logistic models individually adjusted for age, diabetes, chronic lung disease/moderate or severe asthma, immunocompromise, liver disease, heart disease/hypertension, smoking and obesity (BMI  $> 40$ ), residence in long-term care facility, will also be examined with odds ratios and 95% confidence intervals reported.

The analysis of secondary time to event endpoints including survival at 30 days, duration of hospitalization, duration of ventilation and ventilator free days, will be compared between treatment arms based on a log-rank test. The median will be estimated with a 95% CI for each treatment arm using the Kaplan-Meier method. Cox proportional Hazards models adjusted individually for age, diabetes, chronic lung disease/moderate or severe asthma, immunocompromise, liver disease, heart disease/hypertension, smoking and obesity (BMI  $> 40$ ), residence in long-term care facility, will also be examined with odds ratios and 95% confidence intervals reported. Changes in inflammatory markers and in oxygenation or  $\text{paO}_2/\text{FIO}_2$  ratio, based on available recorded measurements, will be compared between treatment arms using a two sample t-test, or a Wilcoxon Rank Sum test, as appropriate. Incidence of grade 3 or 4 AEs and serious AEs will be compared using Fisher's Exact test.

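### Both adverse-event endpoints and the AE/SAE reporting rule stop at hospital discharge, so the arms are compared over a window set by length of stay, and the grade endpoint leaves out grade 5

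*Combined protocol and SAP*

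**What the plan says.** **Rules that stop at discharge.** Section 9.3: "AEs and SAEs will be reported from the first dose of study drug through hospital discharge". Section 2.5 lists two AE endpoints, "Cumulative incidence of grade 3 and 4 adverse events during hospitalization" and "Cumulative incidence of serious adverse events during hospitalization". Section 7.2 then says "Incidence of grade 3 or 4 AEs and serious AEs will be compared using" Fisher's exact test. It sets no common window and makes no adjustment for time observed.

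**Text that goes further.** Section 4.1 describes a "follow-up period for adverse events that will include the remainder of hospitalization, with additional assessments at days 30 and 60". The Section 6 calendar marks toxicity notation at Day 30. For discharged patients the information is sought from the primary care provider and, failing that, the "participant will be contacted by the research nurse to assess toxicities". A footnote makes this conditional on feasibility. In the calendar, Day 60 appears for mortality only.

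**Expected timing of toxicity.** Section 5.4: "Following a single IV injection, peak myelotoxicity occurs at seven to nine days". Doses are on Days 1 and 4, with optional later doses on Days 8, 11, 18 and 25 (Sections 4.4 and 5.3).

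**Who is observed.** Section 7.2 bases safety analyses on patients who took at least one dose of study treatment, and Section 8.1 defines evaluability for toxicity in the same way. Section 4.1 ends control-arm follow-up for all objectives at death or discharge.

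**The concern.** A between-arm comparison of crude incidence is fair only if both arms are watched for the same time. Here the watch ends at discharge, and duration of hospitalization is itself a secondary endpoint that etoposide is meant to influence. A difference in stay alone can then produce, or hide, a difference in AE incidence. The Day 30 toxicity data that would correct this are planned but feed no endpoint.

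Two features add to it. The expected myelosuppression comes one to two weeks after dosing, so early discharge can close the window before it. And naming grades 3 and 4 only, when Section 9.1 adopts CTCAE version 5.0, leaves a patient whose sole severe event is grade 5 counted as event-free on that endpoint.

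Safety is a stated aim of the trial (Section 2.1), so these are main results rather than supporting tables.

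**Working it through.** The plan gives no AE rate, length of stay by arm, or power for a safety comparison, so there is no safety figure to reproduce.

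**1. When the nadir falls.** Inputs: dose days (Sections 4.4, 5.3) and 7 to 9 days to peak (Section 5.4). Nadir = dose day + 7 to dose day + 9.
- Day 1 dose: Days 8-10. Day 4 dose: Days 11-13.
- Optional doses on Days 8, 11, 18 and 25: Days 15-17, 18-20, 25-27 and 32-34.

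The 7-9 days refer to a single injection, so applying them to each dose is a reading of Section 5.4. A patient in hospital to about Day 13 has the Day 4 nadir covered, because blood counts are at least twice weekly during admission. Only earlier discharges lose it. The last optional nadir falls after the Day 30 visit.

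**2. Which patients can leave early.** Input: the scale in Section 8.2.
- Cohort 1 starts intubated, at level 6 or 7. A two-level gain gives level 4 or 5, still in hospital.
- In cohort 2, a patient at level 5 who gains two levels is at level 3, still in hospital. A patient at level 4 who gains two is at level 2, which means discharged.

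The early-discharge problem therefore sits mainly in cohort 2.

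**3. What a stay-dependent window does (illustration).** Assumptions, not from the documents: the same true 30-day risk R in both arms, a constant hazard, and a fixed stay of d days. Observed risk = 1 − (1 − R)^(d/30).

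| R in both arms | 10 days | 14 days | 21 days | 30 days |
|---|---|---|---|---|
| 30% | 11.2% | 15.3% | 22.1% | 30% |
| 50% | 20.6% | 27.6% | 38.4% | 50% |

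With stays of 10 against 14 days the spurious gap is 15.3 − 11.2 = 4.1 points at R = 30% and 27.6 − 20.6 = 7.0 at R = 50%. With 10 against 21 days it is 22.1 − 11.2 = 10.9 and 38.4 − 20.6 = 17.8. With a common Day 30 window it is zero. A constant hazard after discharge probably overstates these gaps.

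**4. Nadir events captured (illustration).** Assume a share q of the 24 etoposide patients in a cohort have a nadir event, and a share s leave before it. Captured = 24 × q × (1 − s).
- q = 20%: 4.8 events occur; 4.3, 3.4 or 2.4 are captured for s = 10%, 30% or 50%.
- q = 40%: 9.6 occur; 8.6, 6.7 or 4.8 are captured.

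**5. Fatal events.** Section 9.2 says "a SAE is any untoward medical occurrence that results in any of the following outcomes", with death listed first, so an in-hospital death belongs to the SAE endpoint. Deaths to Day 30 belong to the survival endpoint in Section 2.5. What remains is the grade 3-4 count. If a share m of 24 patients die of an event graded 5, and a share f of them had an earlier grade 3-4 event, that count misses 24 × m × (1 − f). For m = 20% this is 2.4, 1.0 or 0 patients at f = 50%, 80% or 100%; for m = 40% it is 4.8, 1.9 or 0. Both shares are assumed.

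**6. Start of the window.** Section 9.3 opens it at the first dose, which controls never receive. For the same reason controls cannot enter the all-treated set, although Section 7.2 asks for a comparison between groups.

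**The case against.** The strongest defence is that little is really lost. Section 9.1 requires all adverse experiences to be recorded, without a grade limit. Inpatient blood counts cover the nadir for anyone still admitted. Toxicity is noted at Day 30. Deaths are SAEs, count in survival, are recorded at Days 14, 30 and 60, and go to the Medical Monitor within 24 hours (Section 10.2). The 9.3 sentence also follows one about reporting to the IRB and FDA, so it may set a regulatory-reporting period rather than end data collection. Cohort 1, where early discharge is less likely, is the only cohort certain to open.

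Most of this stands, and it rules out three stronger readings that a reader might infer:
- *Fatal events drop out of the safety data.* They do not. They are missed only by the grade 3-4 count, and only without an earlier grade 3-4 event. A death after discharge leaves the SAE endpoint but not survival.
- *Neutropenic infection after discharge need never be reported.* The Day 30 contact is there to find it, although only as far as feasible.
- *The nadir is generally missed.* It is missed only for discharges before about Day 11-13. Even a cohort 2 patient who responds by going home may leave on Day 13 or 14.

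The defence does not reach the endpoints. Even if 9.3 is only a regulatory rule, Section 2.5 independently limits both endpoints to the hospital stay, and no analysis uses the Day 30 data.

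**Conclusion.** The point holds as a conflict between sections and a flaw in how the AE endpoints are defined. Sections 2.5 and 9.3 stop at discharge, Sections 4.1 and 6 go on to Day 30, and Section 7.2 compares crude incidence over a window that treatment may change. At equal event rates, shorter stays give fewer counted events, whatever the values.

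A reader might go on to infer that the comparison favours etoposide. The documents do not support that. They give neither AE rates nor stays by arm, and if etoposide lengthened stays the effect would run against it. The gaps of about 4 to 18 points above rest on assumed risks, stays and a constant hazard. They show the mechanism and are not an estimate of bias.

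The grade 5 gap is real but limited to one endpoint. The early-nadir gap is real but falls mainly in cohort 2, which may not open.

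**What to change.** Reconcile Sections 2.5, 4.1, 6, 7.2 and 9.3, with matching wording in 8.1 and 10.1:

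- **Window.** Collect and compare AEs and SAEs in both arms from randomization to Day 30, whether or not the patient has been discharged, using the Day 30 toxicity contact already planned. Start at randomization because controls have no first dose. Remove the 4.1 wording that ends control follow-up at discharge.
- **Safety set.** Redefine it so that controls are included and the comparison in 7.2 is possible.
- **Grade endpoint.** Count grade 3 or higher (3-5). State whether death from progressive COVID-19 is graded as an AE.
- **Analysis.** Report cumulative incidence to Day 30, with death from other causes as a competing event. Where the Day 30 contact fails, censor at last contact and report the number by arm.
- **Optional later doses.** Extend AE capture past Day 30 for these patients, since a Day 25 dose puts the stated nadir at Days 32-34. Report the extra period separately, so that the between-arm comparison keeps one window.

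The cost is protocol and SAP wording and somewhat more event recording after discharge. The remaining weakness is that Day 30 data are obtained only as feasible, so events after discharge may be less complete than those in hospital.

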#### **9.4 Interim Analysis**

Interim analysis will occur after 10 patients are enrolled into cohort 1. Safety data including adverse events and patient outcomes will be presented to the medical monitor (and COVID research committee as detailed in section 4.2). If cohort 2 is activated, an interim analysis will also be performed after 10 patients have enrolled in that cohort.

#### **9.5 Stopping Rules**

Accrual in a cohort will continue after the interim analysis if  $\geq 1$  of the treated patients in that cohort meets the primary endpoint of 2 point improvement in respiratory status on the 8 point scale at day 14. If cohort 1 is stopped, enrollment in cohort 2 (if open) may still continue.

### **10. DATA MANAGEMENT**

#### **10.1 Analyses and Reporting**

Data generated by the methods described in the protocol will be recorded in the subjects' medical records and/or study progress notes. The investigator will be the assessor of the primary endpoint. Data will be directly inputted into an electronic system. Data will be analyzed and reported after study is completed or meaningful endpoints are reached. All subsequent data collected will be analyzed and reported in a follow-up clinical report.

The index data for patients on treatment is the day 1 dose of etoposide. For patients enrolled into the standard of care arm, day 1 will be the day of randomization.

The Principal Investigator at BMC/BU Medical Campus will report Unanticipated Problems, safety monitors' reports, and Adverse Events to the BMC/BU Medical Center IRB and FDA in accordance with established policies:

- Unanticipated Problems occurring at BMC/BU Medical Campus will be reported to the IRB within 7 days of the investigator learning of the event.
- Unanticipated Problems occurring at BMC/BU Medical Campus will be reported to the FDA within 15 days of the investigator learning of the event.
- Unexpected fatal or life-threatening suspected adverse events occurring at BMC/BU Medical Campus will be reported to the IRB within 7 days of the investigator learning of the event.
- Reports from the designated medical monitor with recommended changes will be reported to the IRB within 7 days of the investigator receiving the report.
- Adverse Events (including Serious Adverse Events) will be reported in summary at the time of continuing review, along with a statement that the pattern of adverse events, in total, does not suggest that the research places subjects or others at a greater risk of harm than was previously known.

- Reports from designated medical monitor with no recommended changes will be reported to the IRB at the time of continuing review.

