### **2. STUDY PLAN**

#### **2.1 Study Design**

This is a randomized, open-label phase II study designed to evaluate the safety and efficacy of etoposide in patients with COVID-19 infection. Treatment will be comprised of etoposide administered intravenously at a dose of 150 mg/m^2 on Days 1 and 4 in patients with COVID-19 infection meeting eligibility criteria. Subsequent doses of etoposide will be allowed if the investigator and treating physician believe the patient had clinical benefit from etoposide therapy but subsequently has evidence of recurrent clinical deterioration.

Two cohorts of patients will be treated with etoposide. Cohort 1 will be patients who require intubation due to their severe COVID-19 related respiratory illness. Cohort 2 will be COVID-19 patients who have progressive pulmonary dysfunction and evidence of severe inflammation but who are not yet intubated. Although prior treatment for COVID with anti-cytokine therapy will not exclude a patient from enrollment on this trial, a “washout” period of at least 3 half-lives will be required prior to initiation of etoposide therapy. Enrollment will begin with cohort 1, following which a decision will be made to open cohort 2 or not, as outlined further in this document.

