### **3.2 Inclusion Criteria (applicable for patients enrolled for treatment or data collection)**

- Age 18 years or older
- Confirmed COVID-19 infection
- Evidence of cytokine storm defined as:
  - Peak ferritin > 10,000 ng/mL OR
  - Peak ferritin > 500 ng/mL and one or more of the following at any time during hospital admission:
    - Lactate dehydrogenase > 500 U/L, d-dimer > 1000 ng/mL, C-reactive protein > 100 mg/L, or WBC > 15 k/uL
- Cohort 1: Intubated status as a result of COVID infection-associated respiratory illness
- Cohort 2 (if activated): Evidence of progressive respiratory failure (requiring >4 L/min of supplemental oxygen to maintain SaO2 greater than 92%) without intubation

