## 7. STATISTICAL CONSIDERATIONS

### 7.1 Sample Size Considerations

This study will be performed with two cohorts 1) severe COVID-19 infection and 2) moderate COVID-19 infection (as defined in inclusion criteria).

The effect of the intervention will be evaluated in each cohort separately. A total of 32 patients will be enrolled in each cohort with a 3:1 allocation ratio (24 Etoposide and 8 control per cohort). Assuming a 30% response rate in the control group for the primary outcome of a 2 point improvement in respiratory status on an 8 point scale at Day 14, we can detect a 50% increase in response in the Etoposide group (80% response rate in the Etoposide group) with a 2-sided  $\alpha$  of 0.05 and 80% power. While this study is not powered to detect a statistically significant difference in outcome, it will provide initial evidence of efficacy if improvement in response is observed.

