## 8.2 Response Definitions

8-Point Ordinal Scale:

- 8 - Death;
- 7 - Ventilation in addition to extracorporeal membrane oxygen (ECMO), continuous renal replacement therapy (CRRT), or need for vasopressors (dopamine  $\geq 5$   $\mu$ g/kg/min OR epinephrine  $\geq 0.1$   $\mu$ g/kg/min OR norepinephrine  $\geq 0.1$   $\mu$ g/kg/min);
- 6 - Intubation and mechanical ventilation;
- 5 - Non-invasive mechanical ventilation (NIV) or high-flow oxygen;
- 4 - Hospitalized, requiring oxygen by mask or nasal prongs;
- 3 - Hospitalization without oxygen supplementation;
- 2 - Discharged from hospital either to home with supplemental oxygen OR to inpatient rehabilitation/skilled nursing facility (+/- supplemental oxygen);
- 1 - Discharged to home without supplemental oxygen

When calculating Ventilator Free days, reintubations or re-hospitalizations or death occurring in the first 28 days should result in zero ascribed to time off the ventilator prior to reintubation

When calculating days of hospitalization, re-hospitalization or death occurring in the first 28 days should result in zero ascribed to time out of the hospital prior to readmission.

When determining days of supplemental oxygen use and need for supplemental oxygen, the patient will only be considered to no longer need supplemental oxygen if a room air saturation is  $\geq 90\%$  after five minutes of rest.

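### The unmasked investigator scores the primary endpoint, and an undefined line between categories 5 and 4 decides response for some cohort 1 patients

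*Combined protocol and SAP*

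**What the plan says.** Section 2.1: "This is a randomized, open-label phase II study". Section 4.1 adds: "No placebo will be used".

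Section 7.1 gives the endpoint as the "primary outcome of a 2 point improvement in respiratory status on an 8 point scale at Day 14". Section 10.1 names who scores it: "The investigator will be the assessor of the primary endpoint". No section provides a masked assessor, adjudication or a second reader. The Medical Monitor in section 10.2 has a safety remit, and the COVID Research Committee in section 4.2 decides whether cohort 2 opens.

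The two categories at issue in section 8.2 are "5 - Non-invasive mechanical ventilation (NIV) or high-flow oxygen" and "4 - Hospitalized, requiring oxygen by mask or nasal prongs". Neither carries a flow rate, an inspired oxygen fraction or a device list. No rule says which time counts for a patient who changes support during the day.

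Entry to cohort 1 (section 3.2) requires "Cohort 1: Intubated status as a result of COVID infection-associated respiratory illness". The calendar in section 6 schedules the respiratory score at screening, on Days 1, 4 and 7, before discharge and at Day 30. For Day 14, the primary time point, its footnote adds only mortality.

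**The concern.** Category 5 is defined partly by flow and category 4 by interface, so the two are not mutually exclusive. High flow delivered through a mask or nasal prongs can be read as either. For a patient who started at 6, that reading decides whether the patient counts as a responder, and the reader knows the treatment.

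The risk is differential misclassification: doubtful cases may be scored more favourably in one arm than in the other. Analysing all randomized patients and using Fisher's exact test does not correct this, because the error enters before the counts are formed. The missing Day 14 score adds to the problem, since the category at the primary time point may have to be reconstructed from the chart by someone who is not masked.

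**Working it through.** **1. Which patients are exposed.** Response is a drop of 2 or more categories.
- Baseline 6: response needs 6 − 2 = 4 or lower. Category 5 is a non-response, so the 5/4 line decides.
- Baseline 7: response needs 7 − 2 = 5 or lower. The deciding step is 6 to 5, which is extubation, so the 5/4 line does not matter. Such patients can enter: section 3.3 excludes only those needing more than one vasopressor, and category 7 includes ventilation with one vasopressor at the listed doses.
- Death, continued intubation, no oxygen and discharge at Day 14 are not touched by the 5/4 line.

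The exposed group is therefore patients with baseline 6 who are extubated, in hospital and on oxygen at Day 14. The documents give neither the baseline distribution nor the size of this group.

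**2. Whether another rule closes the gap.** The room-air saturation rule in 8.2 settles only whether oxygen is still needed. The only oxygen flow figure, above 4 L/min in section 3.2, is a cohort 2 entry criterion. Neither separates 5 from 4.

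**3. The plan's own figure.** The plan states no misclassification rate. Its related figure is 80% power in section 7.1 for 80% v 30% with 24 v 8. The unpooled normal approximation comes close:
- SE = √(0.3×0.7/8 + 0.8×0.2/24) = 0.181
- power = Φ(0.5/0.181 − 1.96) = 78.7%

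The expected counts are 0.8×24 = 19.2 and 0.3×8 = 2.4, so 19/24 v 2/8 represents the planned rates.

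**4. Weight of one call.** One control is 1/8 = 12.5 points. One etoposide patient is 1/24 = 4.2 points. Two-sided Fisher p-values, the planned test (section 7.2):

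| Etoposide | Control | Difference | p |
|---|---|---|---|
| 16/24 | 2/8 | 66.7 − 25.0 = 41.7 points | 0.096 |
| 17/24 | 2/8 | 70.8 − 25.0 = 45.8 points | 0.038 |
| 18/24 | 2/8 | 75.0 − 25.0 = 50.0 points | 0.030 |
| 19/24 | 2/8 | 79.2 − 25.0 = 54.2 points | 0.010 |
| 19/24 | 3/8 | 79.2 − 37.5 = 41.7 points | 0.072 |

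Rows 1 and 2 differ by one etoposide call. Rows 4 and 5 differ by one control call. These tables are illustrations; the first pair was chosen because it lies at the 0.05 edge.

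**5. A rate-based illustration.** Assume true response is 30% in both arms and a share u of etoposide non-responders is scored as responders. The recorded etoposide rate is then 0.3 + 0.7u. Summing the binomial probabilities of all 9 × 25 = 225 possible tables with Fisher p ≤ 0.05 favouring etoposide gives:

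| u | Recorded rate | Chance of a significant result for etoposide |
|---|---|---|
| 0 | 30% | 1.0% |
| 10% | 37% | 2.8% |
| 20% | 44% | 6.3% |
| 30% | 51% | 12.2% |

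The documents give no value for u. Only non-responders at the boundary could contribute to it.

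**6. Interim.** Section 9.5 continues accrual if at least one treated patient meets the primary endpoint. If there is no other responder, one call of 4 rather than 5 satisfies the rule.

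**The case against.** The strongest reply is that the exposed group is narrow and of unknown size. That stands. A reader might infer that cohort 1 response as a whole depends on the 5/4 line. The documents do not support this, because patients can enter at category 7 and most other categories are largely objective.

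A reader might also extend the point to cohort 2. That is not supported either. From baseline 5 the deciding step is 4 versus 3, for which 8.2 has the room-air saturation rule. The 5/4 line enters only through the baseline score. The calendar includes a screening score, before the arm is known. The protocol does not say whether screening or Day 1 is the baseline, but a differential error there is not established.

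One-patient flips occur in any 24 v 8 comparison and do not measure assessor bias. That stands as well: at 19/24 v 2/8, three etoposide responders must be lost before significance goes (16/24, p=0.096). A single control call is still enough (p=0.072).

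Finally, this is a small phase II study that discloses investigator assessment, keeps its source documents open to audit and says it is not powered for significance. Yet section 7.2 plans a formal Fisher comparison, and section 7.1 intends an observed improvement as initial evidence of efficacy. An audit can check the source record, but without a written limit there is no standard against which to check a 5/4 call.

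**Conclusion.** The point holds for a defined subgroup: cohort 1 patients with baseline 6 who at Day 14 are extubated, in hospital and on oxygen. For them an undefined boundary, applied by an assessor who knows the arm, decides the primary endpoint. Each such call is worth 12.5 points in the control arm or 4.2 points in the etoposide arm, and one call can be enough to cross 0.05. How often this would occur cannot be estimated from the documents. The p-values assume full cohorts of 24 and 8 and are illustrative.

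A reader might conclude that biased scoring took place or that the result would be invalid. The documents show the opportunity for bias, not its occurrence. The correction is worth making because it is cheap and removes the discretion at the scoring step.

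**What to change.** - **Section 8.2:** before any scoring, fix a device-and-flow list that separates category 4 from category 5, and state one scoring-time rule for the day. The worst category in the calendar day is one possible convention.
- **Section 6:** add respiratory support status at Day 14, where the calendar now lists only mortality.
- **Section 10.1:** replace investigator assessment with derivation of the category by a fixed program. Its inputs are charted device, flow or inspired oxygen fraction, vasopressor, CRRT and ECMO use, discharge disposition and vital status. Run it on an extract without the arm column. The investigator supplies source data only.
- **Assignment:** name who runs the program. Because the rule is programmed, existing study personnel can do this and no extra assessor is needed. Section 10.2 mentions a data analyst but does not give that person this task, so the protocol must assign it.

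The cost is about half a page of rules, a short program and a few data queries where flow is not charted. The benefit is partial, since open-label influence on care decisions, including the choice of oxygen device, would pass into the derived score. The change concerns scoring only, not which oxygen support patients receive.
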